4. STUDY OBJECTIVES

The objective of this study is to demonstrate the safety and effectiveness of the BAROnova TransPyloric Shuttle for weight reduction in patients with BMIs of 30-40 kg/m² compared with the sham-control over the 12 months treatment period.

The study will also assess, as secondary endpoints, changes in weight-related comorbidities, weight-related quality of life, and eating behavior.

The study will be considered a success for efficacy purposes if it meets both of the primary efficacy analyses.

The safety will be characterized, with all adverse events reported. The Clinical Event Committee (CEC) will adjudicate all serious device-related adverse events and any other events deemed necessary.

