7.4. Point of Enrollment

The point of enrollment occurs when a subject or subject's legally authorized representative has provided written informed consent and the TPSS Access Sheath has been introduced in the subject during the index procedure.

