11.9.3. Index Procedure (Day 0)

The TPS placement procedure will be performed under general or monitored anesthesia care (MAC). Eligible subjects will undergo standard preparation for an endoscopic procedure, followed by an endoscopic assessment of the esophagus, stomach, antrum, pylorus and duodenum. Subjects who meet the endoscopic exclusion criteria will be considered an endoscopic screening failure and excluded from the study.

Subjects who do not possess any endoscopic exclusion criteria will be randomized into Treatment or Control group using a web-based randomization system provided by the study data management organization. Procedure details can be found in the instruction for use (IFU). In brief, a TPSS Access Sheath is inserted over the gastroscope using standard techniques to position the distal tip approximately 6 cm below the gastroesophageal junction. Endoscopic visualization is used to monitor inflation of the distal positioning balloon on the Access Sheath and confirm final insertion position. After removal of the gastroscope and obturator, the TPS Delivery Device is lubricated and inserted into the Access Sheath until fully-seated with the connectors engaged. The TPS Delivery Device is placed on the TPSS Stand and connected to the insufflation system. Deployment of the TPS is accomplished by forward rotation of TPS Advance Torque Knob on the delivery device handle. Following actuation of the TPS locking mechanisms on the TPS Delivery Device, the formed TPS is released into the stomach and the Access Sheath and TPS Delivery Device are withdrawn from the patient. A final endoscopic evaluation is performed to inspect the final device configuration and assess the gastroesophageal tissues prior to completion of the procedure.

In the Control subject, the sham procedure consists of anesthesia and the TPSS Access Sheath placement but no TPS delivery. Effort will be made so that the overall sham procedure time is similar to the TPS placement procedure time.

Subject will be discharged when the site and physician's discharge criteria are met (if designated by the hospital policy and procedures).

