15.2. Analysis Populations

The following analysis populations are defined for the study: Intent-to-Treat (ITT), modified Intent-to-Treat (mITT), Per-Protocol (PP) and Completed Cases (CC). The primary effectiveness hypotheses will be tested on the PP population. The primary safety analysis will be performed on mITT population. The ITT and CC populations will be used in a sensitivity analysis of the primary effectiveness endpoint.

- Intent-to-Treat: The Intent-to-Treat population includes all randomized and enrolled subjects as defined in Section 7.4 regardless of whether or not the subject received the randomized treatment.
- Per-Protocol: The Per-Protocol population is a subset of the ITT population and includes all subjects who receive the assigned treatment and do not have any major eligibility violations.

- **Modified Intent-to-Treat:** The mITT population consists of the ITT population subjects who received the assigned treatment and that have at least one post-treatment follow-up, including the index procedure visit.
- **Completed Cases:** The CC population includes all enrolled subjects who have the 12-month follow-up visit, or have completed the study based on reaching the BMI objective of $\leq 22 \text{ kg} / \text{m}^2$ in two consecutive follow-up visits as described in Section 5.1.

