15.3.2. Safety Objective

The objective of the safety analysis is to provide safety information sufficient to characterize and summarize adverse events observed during the study.

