15.5.5. Safety Analysis

The safety analyses will be performed using the mITT Population.

An overall summary of AEs will be provided including the number of events and percent of subjects with any AEs, SAEs, and UADEs. For each type of event, the number of events and number and percent of subjects with the event will be provided in a table. Separate summaries of all adverse events will be summarized by relationship to device and procedure. Adverse events will be coded using MedDRA medical dictionary.

15.5.6. [REDACTED]

[REDACTED]

[REDACTED]

[REDACTED]

[REDACTED]

[REDACTED]

[REDACTED]

[Redacted]

15.5.7. [Redacted]

[Redacted]

[Redacted]

[Redacted]

[Redacted]

[Redacted]

[Redacted]

[Redacted]

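### Safety tables use a population that requires receipt of the assigned treatment, so a Treatment subject whose device delivery fails, even through injury, is left out

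*Combined protocol and SAP*

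**What the plan says.** Section 15.2 assigns the safety analysis to mITT: "The primary safety analysis will be performed on mITT population". Section 15.5.5 says the same without the word primary: "The safety analyses will be performed using the mITT Population". No other safety population is named in the legible text.

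Within the ITT set, mITT consists of "subjects who received the assigned treatment and that have at least one post-treatment follow-up, including the index procedure visit". ITT itself keeps randomized and enrolled subjects "regardless of whether or not the subject received the randomized treatment".

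Enrollment requires consent and that "the TPSS Access Sheath has been introduced in the subject during the index procedure" (section 7.4). Sections 5.2 and 11.9.3 place TPS delivery after the sheath, in the Treatment group only. For Controls, "the sham procedure consists of anesthesia and the TPSS Access Sheath placement but no TPS delivery" (section 11.9.3).

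On the purpose of the safety evaluation, section 4 says: "The safety will be characterized, with all adverse events reported". Section 15.3.2 sets the objective as information sufficient to "characterize and summarize adverse events observed during the study".

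**The concern.** Safety in this trial has no hypothesis test (section 6.3). It rests on descriptive counts, which are then weighed against effectiveness (section 12), so the counts need to be complete. Under the stated rule, membership of the safety set can depend on the harm being counted: an injury during the procedure can be the reason delivery stops, and stopping delivery takes the subject and the injury out of the tables.

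The plan allows for such cases. The ITT definition provides for subjects who did not receive their treatment, section 3.5.2 lists digestive tract injury from the delivery system as an anticipated event, and section 19.2 covers devices involved in a procedural failure.

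The loss is also uneven between arms. A Control has received the full assigned treatment once the sheath is in place, so harm that stops delivery after that point can remove Treatment subjects only. Harm before full sheath placement could exclude a subject from either arm, and no difference between arms is claimed for that stage.

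**Working it through.** **Who is in which set.**

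1. Sheath introduced, after consent and randomization: the subject is enrolled and in ITT (sections 7.4, 15.2).
2. The assigned treatment in the Treatment group is TPS placement (section 5.1), which comes after step 1.
3. mITT joins two conditions with *and*: treatment received, and at least one follow-up. Counting the index visit as follow-up relaxes only the second.
4. A Treatment subject whose delivery fails after step 1 meets the follow-up condition but not the treatment condition, so is in ITT and not in mITT.

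**The plan's own safety figures (section 15.4, n = 180).**

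- Chance of at least one event at a true rate of 0.9%: 1 − (1 − 0.009)^180 = 80.4%. The plan states 80%.
- Upper two-sided 95% exact limit with no events: 1 − 0.025^(1/180) = 2.03%. The plan states 2.0%.

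Both reproduce.

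**How many subjects could be excluded.** No placement failure rate is given for this device generation. The feasibility study of the previous generation had 20 of 20 deployed (section 3.4.3). The 95% upper limit for failure from 0/20 is 1 − 0.025^(1/20) = 16.8%, so that experience rules out little. The rate *q* is therefore an assumption. Expected exclusions are 180*q*, and the chance of at least one is 1 − (1 − *q*)^180:

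| Assumed *q* | Expected excluded | Chance of at least one |
|---|---|---|
| 0.5% | 0.9 | 59% |
| 1% | 1.8 | 84% |
| 2% | 3.6 | 97% |
| 5% | 9.0 | >99.9% |

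These are excluded subjects, not injuries. The share injured is not known.

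**Effect on the denominator.** This is negligible. The zero-event upper limit moves from 2.03% (n = 180) to 2.13% (n = 171).

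**Effect on the numerator.** Suppose *k* subjects have a failed delivery with a given injury and nobody else has that injury (exact 95% limits):

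| *k* | mITT table | Upper limit shown | All enrolled | 95% CI |
|---|---|---|---|---|
| 1 | 0/179 | 2.04% | 1/180 = 0.56% | 0.01–3.06% |
| 2 | 0/178 | 2.05% | 2/180 = 1.11% | 0.13–3.96% |
| 4 | 0/176 | 2.07% | 4/180 = 2.22% | 0.61–5.59% |
| 9 | 0/171 | 2.13% | 9/180 = 5.00% | 2.31–9.28% |

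In the rows *k* = 4 and *k* = 9, the observed rate among enrolled subjects exceeds the upper limit that the mITT table would show. These rows are extreme, because every failed delivery is taken to involve the injury.

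**The case against.** **Received may mean underwent the procedure.** The term is not defined. Counting the index visit as follow-up suggests a wish to keep everyone who had the procedure, and Appendix A defines the index procedure by placement or sham placement. This reading is possible but strained: the ITT definition in the same section treats being enrolled and having received the treatment as separate states. If it is what the sponsor means, the text still needs changing to say so.

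**The event would not vanish.** Adverse events during the procedure are collected (section 11.9.3) and recorded on the eCRF (section 12.3.2). Serious events go to the sponsor, cumulative safety data go to the DSMB (section 14), and section 15.5.1 would show the gap between the ITT and mITT counts by arm. All this stands and limits the consequence. None of it puts the events into the section 15.5.5 tables. The CEC's classifications feed the final safety analyses, which are themselves on mITT.

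**The size is speculative.** Harm is lost only if failure and injury coincide. If, as an illustration, 10% of failures involved injury, the chance of at least one lost injury among 180 is 1 − (1 − 0.001)^180, about 16%, at a 1% failure rate, and 1 − (1 − 0.005)^180, about 59%, at 5%. This is fair, and the size remains open.

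**An all-enrolled set dilutes residence events.** Subjects who never carried a TPS would enter the denominator for events such as ulcers. That is correct: with 9 of 180 unplaced, such rates fall by 5% relative, and at a 1% failure rate by about 1%. Keeping mITT as a supportive table meets the point.

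**Redaction.** Sections 5.4, 5.5, 15.5.6 and 15.5.7 are blacked out, and the staged safety monitoring may use another denominator. That does not alter section 15.5.5, which is legible.

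**Conclusion.** The concern holds on the wording of sections 15.2 and 15.5.5. The safety population can drop subjects because of the harm it is meant to count and, after full sheath placement, only from the Treatment arm. This does not fit the aims stated in sections 4 and 15.3.2. The direction is known: the tabulated Treatment complication count can only be too low. The size is not known, since it depends on a failure rate and an injury share that the documents do not give. The smallest case is one missing event, 0/179 instead of 1/180. The conclusion assumes the natural reading of received as completed TPS delivery. Neither co-primary analysis nor the success criterion is touched, so this should be fixed but does not threaten the trial's main result.

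**What to change.** In sections 15.2 and 15.5.5:

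- Base all safety analyses on the randomized and enrolled subjects, meaning those with the Access Sheath introduced. This is the ITT set already defined.
- Count every subject randomized to Treatment in the Treatment group, whether or not TPS delivery was started or completed.
- Count any Control who received a TPS as device-exposed, with the Treatment group.
- Tabulate failed or abandoned placements by arm, with their adverse events.
- Keep mITT as a supportive table, so that rates of device-residence events can be read among subjects who received the TPS.

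The cost is a small rewording and one new table, with the mITT summary kept as support. No extra subjects, visits or data items are needed, because adverse events at the index procedure are already collected. Reported event rates may look slightly less favourable.

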15.3. Study Objectives and Hypotheses

15.3.1. Primary Effectiveness Objective

The primary objective of this study is to assess the clinical effectiveness of the BAROnova TransPyloric Shuttle for weight reduction in patients with obesity, with a BMI of 35.0 to 40.0 kg/m², or a BMI of 30.0 through 34.9 kg/m² with one or more obesity-related comorbid conditions over the 12 months treatment period.

The hypothesis associated with the first co-primary endpoint is that the subjects in the Treatment group will have superior weight loss in %TBL compared to subjects in the Control group at 12-month follow up. The statistical null and alternative hypotheses are:

$$H_{i0}: \mu_T - \mu_C \leq \delta \text{ vs.}$$

$$H_{iA}: \mu_T - \mu_C > \delta,$$

Where,

μ_T is the mean % TBL at 12 months in the treated group

μ_C is the mean % TBL in the control group at 12 months.

δ is the superiority margin.

The hypotheses will be tested using a one-sided two-sample t-test for independent samples at the alpha level of 0.025. If the test value exceeds the nominal critical point, the H₀ will be rejected. The testing may be performed using mixed model repeated measurements approach. If the mixed model is used, the decision about the rejection of null hypothesis will be based upon the test for the 12-month follow-up outcomes. The primary statistical test will use $\delta = 0$. If the H₀ is rejected, the 95% confidence interval for the difference in %TBL between the groups will be created. The lower limit of the interval is the statistically achieved superiority margin.

The second co-primary effectiveness endpoint is the percentage of Treatment subjects with a $\geq 5\%$ TBL at 12 months. Proportion of subjects who lose at least 5% of their baseline weight will be compared against the target proportion of 50% using a one-sided test for hypothesized population proportion.

The statistical null and alternative hypotheses are:

$$H_{ii0}: p_T < \Pi_0 \text{ vs.}$$

$$H_{iiA}: p_T \geq \Pi_0,$$

Where,

p_T is the proportion in the study subjects from the Treatment group

Π_0 is the reference proportion (i.e 0.5 (50%))

Study statistical success is achieved if study null hypotheses for both co-primary endpoints are rejected. FDA recommends that the H_{i0} is rejected with superiority margin $\delta = 5\%$ and the H_{ii0} is rejected.

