5.3. Randomization and Masking

Eligible subjects will be randomized to either the Treatment or the Control group in a 2:1 ratio stratified according to center. Randomization will be according to a random permuted block design within strata. Block size of 3 and 6 will be used.

Randomization occurs on the day of the procedure after endoscopic screening. The Investigator who performs the index procedure and endoscopic follow-ups will not collect the primary outcome data. The Investigator and/or the study coordinator who collect the primary outcome data will be masked to the subject's intervention.

The subject will be blinded to the intervention for the duration of participation in the study.

The Clinical Event Committee (CEC) will be masked to the subject’s intervention. The Data Safety Monitoring Board (DSMB) will have access to unmasked subject data, as required, to monitor and evaluate the safety data throughout the study.

5.4. [REDACTED]

[REDACTED]

[REDACTED]

[REDACTED]

[REDACTED]

[REDACTED]

5.5. [REDACTED]

[REDACTED]

[REDACTED]

[REDACTED]

[REDACTED]

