15.4. Sample Size Considerations

A total sample size of 270 subjects is planned for the pivotal study cohort. The ENDObesity I study provided estimates for the mean %TBL of 14.5 (SD=5.8) at 6 months of follow-up. For the purposes of the sample size calculation, the assumed means were 13% in Treatment and 5% in Control subjects. This provides a difference (Treatment – Sham Control) in mean %TBL of 8% and the assumed standard deviation was increased to 9% (approximately 1.5 times that observed in the ENDObesity I study) to account for a more conservative estimate of the standard deviation. Under these assumptions, a sample size of 243 subjects (162 Treatment, 81 Control) has 90% power to reject H_0 under the 4% superiority margin scenario and 68.4% power under the superiority margin of 5%. Under less conservative scenario of standard deviation of 7, the study has 88% power to reject H_0 under the 5% superiority margin scenario and 99% power under the 4% superiority margin. The study will enroll 270 subjects (approximately 180 in the Treatment groups and 90 in the Control group) to compensate for losses to follow-up.

The second co-primary endpoint is to demonstrate the proportion of subjects with a $\geq 5\%$ TBL at 12 months is greater than 50%. Under the assumption of 65% responder rate in the Treatment group, the study requires 113 treatment subjects in order to have 90% power to reject null hypothesis for the second co-primary endpoint.

A third consideration for the sample size is the ability to provide reasonable safety data from the study. With the proposed sample size of 180 subjects in the Treatment group, there is an 80% likelihood to observe at least one event of any specific complication if it occurs in at a rate of 0.9% or greater in subjects treated with the TPSS. The upper limit of 95% exact binomial confidence interval for an event rate if none of 180 subjects has specific complication is 2.0%.

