15.5.8. Assessment of Poolability

The poolability of the study results across study sites will be assessed. A regression model with covariates for study site, treatment group, and site*treatment interaction will be fit. Study sites with fewer than 10 subjects will be combined into a single pseudo-site for this analysis. If the p-value for the site*treatment interaction term is < 0.10 , this will be considered statistical evidence of a potential differential treatment effect by site.

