16.6. Maintain Blinding during the Study

Only the data management organization and the unblinded statistician have access to the randomization code. The Sponsor's study management team, the Study Steering Committee, the CEC, and the statistician who is responsible for study design and data analysis will be blinded to subject's treatment during the study. The monitors from the monitoring organization will have access to subjects' treatment information in order to perform study monitoring and source data verification.

At each site, the Investigator who performs the index procedure and endoscopic follow up will not collect the outcome data. The Investigator or study coordinator who collects outcome data will be masked. Source documents containing subject treatment information will be either masked or access-controlled according to each site's practice. Each site's blinding procedure will be assessed by the study monitors at the monitoring visits.

In exceptional circumstances when knowledge of the Investigational Device is essential for patient safety in case of serious adverse event, the blinding for this subject may be broken.

The Investigator should promptly (within 24 hours) document and explain to the Sponsor any premature unblinding (e.g., accidental unblinding, unblinding due to a serious adverse event) of the study subject.

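### Randomisation is stratified by centre, but the default test and interval for co-primary 1 leave centre out, so the reported superiority margin is less precise and slightly lower than it need be; the optional mixed model is also unspecified

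*Combined protocol and SAP*

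**What the plan says.** Section 5.3 (and 5.1) sets the design: "Eligible subjects will be randomized to either the Treatment or the Control group in a 2:1 ratio stratified according to center". Blocks are of size 3 and 6, and there are up to 12 sites.

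Section 15.3.1 gives the default test: "The hypotheses will be tested using a one-sided two-sample t-test for independent samples at the alpha level of 0.025". It has no centre term. The formal margin is zero. If the null is rejected, a 95% confidence interval for the difference is formed, and "The lower limit of the interval is the statistically achieved superiority margin". The same section records that FDA recommends rejection at a margin of 5%.

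Section 15.3.1 also says: "The testing may be performed using mixed model repeated measurements approach". If that model is used, its 12-month contrast decides. No condition for using it, no fixed effects and no covariance structure are given.

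Section 15.5.3 tests both co-primary hypotheses on multiply imputed data. It names gender as an example of an imputation covariate and does not mention centre. Centre appears in a model only in 15.5.8: "A regression model with covariates for study site, treatment group, and site*treatment interaction will be fit". That assessment does not feed the primary test. Sections 15.5.6 and 15.5.7 are redacted and cannot be judged.

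**The concern.** Stratifying by centre balances the arms within centre. If centres differ in mean weight loss, that balance removes between-centre variation from the true error of the treatment difference. A pooled t-test still counts that variation in its standard error, so its interval is wider than the design warrants.

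For the zero-margin test this hardly matters. It matters more for the lower confidence limit, which the plan treats as a named result, and for the 5% margin, where section 15.4 states only "68.4% power under the superiority margin of 5" percent at SD 9 (88% at SD 7).

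The second issue is that two tests are available for one hypothesis and nothing says which will be used or when that is settled. If both were seen first, the choice could favour the better result.

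**Working it through.** **Inputs from section 15.4.** Means 13% and 5% (difference 8); SD 9, or 7 in the less conservative case; 162 Treatment and 81 Control. The one-sided alpha of 0.025 is from 15.3.1. The share *v* of %TBL variance lying between centres is not in the documents, so it is an assumption: 0, 2%, 5% and 10%. Twelve centres are assumed, the maximum allowed.

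**1. Reproduce the plan's power.** SE = SD × √(1/162 + 1/81) = 9 × 0.13608 = 1.2247. With 241 degrees of freedom the noncentral t gives 90.2% at margin 4 and 68.4% at margin 5. At SD 7 it gives 88.0% at margin 5 and 98.7% at margin 4. These agree with 15.4, so the stated powers are those of the unadjusted t-test.

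**2. Interval without centre (SD 9).** Half-width = 1.9699 × 1.2247 = 2.41. At an observed difference of 8 the lower limit is 8 − 2.41 = 5.59. An observed difference of at least 7.41 is needed for a lower limit of 5.

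**3. Interval with centre (SD 9).** SE = 1.2247 × √(1 − v), on 241 − 11 = 230 degrees of freedom (t = 1.9703).

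| Centre share v | Half-width | Lower limit at 8 | Power at margin 5, centre in model | One-sided error of the unadjusted t-test |
|---|---|---|---|---|
| 0 | 2.41 | 5.59 | 68.4% | 0.0250 |
| 2% | 2.39 | 5.61 | 69.3% | 0.0239 |
| 5% | 2.35 | 5.65 | 70.6% | 0.0222 |
| 10% | 2.29 | 5.71 | 73.0% | 0.0194 |

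The last column is 1 − Φ(1.96/√(1 − v)). It never exceeds 0.025. At SD 7, power at margin 5 with centre is 88.7%, 89.6% and 91.1% for shares of 2%, 5% and 10%.

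**4. Both tests on the same simulated data.** The settings were N = 243, 12 centres of assumed size 7 to 40, blocks of 3 and 6, sites under 10 pooled, and 30,000 runs per setting. Power at margin 5 (SD 9), t-test then adjusted, was 68.5% and 68.2% at v = 0, 68.7% and 70.2% at 5%, and 69.2% and 72.5% at 10%. So the cost if centre explains nothing is about 0.3 point, and the gain at 10% is about 3 points.

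**5. Margin zero.** Unadjusted power at SD 9 exceeds 99.99%, so centre makes no practical difference there.

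**6. Open choice of test.** Suppose the better of the t-test and a covariate-adjusted contrast is taken after seeing both. In simulation (SD 9, no treatment effect, centre and baseline shares of 0 to 10% each), one-sided error for co-primary 1 alone is 0.027 to 0.031. Treating the two statistics as bivariate normal gives 0.030, 0.032 and 0.035 for assumed correlations of 0.98, 0.95 and 0.90. Requiring both co-primaries cuts the study-level error to 0.004 to 0.005 if both arms average the plan's 5% control mean. It reaches 0.025 only if both arms average about 7% or more.

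Co-primary 2 gives no such protection for a claim at the 5% margin. On that boundary, with Control at 5%, Treatment averages 10%. Then Φ(5/9) = 71% of Treatment subjects reach 5% TBL (normal outcomes, SD 9), and co-primary 2 passes with probability 0.9999 at 162 subjects.

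**The case against.** The strongest reply is that nothing in the plan's own success rule is harmed. Section 4 says: "The study will be considered a success for efficacy purposes if it meets both of the primary efficacy analyses". The test of co-primary 1 uses a margin of zero, the 5% margin is recorded as an FDA recommendation, and the t-test errs on the safe side. This stands: centre adjustment is a gain in precision, not a correction of an invalid test.

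Three stronger readings are tempting, and the documents support none of them.

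- **Leaving out centre makes a margin easier to claim or inflates type I error.** The direction is the opposite: the interval is wider and the lower limit falls.
- **The 68.4% power is caused by omitting centre.** It follows from the sample size, the SD and the margin, and 15.4 discloses it. The t-test's power does not fall below it as the centre share rises. The plan only forgoes a possible gain.
- **Much larger gains are available by also adjusting for baseline.** Those need an assumed baseline share that may be small, because %TBL is already scaled to baseline weight and BMI is restricted to 30 to 40. Section 15.5.3 lists baseline BMI only for descriptive summaries.

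On the mixed model, the plan does name a default and does fix the 12-month contrast. Section 16.6 adds that "the statistician who is responsible for study design and data analysis will be blinded" during the study. A mixed model without covariates and with unstructured covariance, run on completed data, would reproduce the t-test. The error of about 0.03 therefore needs both selection after seeing the results and a covariate-adjusted model that the plan does not describe. What remains is that nothing requires the choice to be fixed before unblinding.

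The calculations also use 243 complete outcomes, whereas the planned analysis is per-protocol with multiple imputation, so the exact figures are illustrative.

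**Conclusion.** The point holds as a modest, nearly free improvement. The default analysis of co-primary 1 does not reflect the randomisation stratum. The result is a valid, slightly conservative test and a lower limit about 0.02 to 0.12 points below what the design could deliver for assumed centre shares of 2 to 10%, against a half-width of 2.41 at SD 9. At a 10% share this changes the conclusion at the 5% margin only if the observed difference falls between about 7.29 and 7.41. The textual facts are certain; the size of the gain depends on a centre share that the documents do not give.

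The unspecified mixed model is a separate gap and the only part that could raise error, to about 0.03 for co-primary 1 under selection after the fact. A reader might infer that the study-level error is inflated to the same degree. That does not follow for the zero-margin success rule at the plan's 5% control mean, because co-primary 2 must also be met.

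**What to change.** Before unblinding, state one primary test in 15.3.1 and 15.5.3:

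- In each imputed data set, fit a linear model of 12-month %TBL on treatment and centre, pooling sites with fewer than 10 subjects as in 15.5.8.
- Combine the estimates by Rubin's rules, and take both the one-sided 0.025 test and the 95% interval for the achieved margin from this model.
- Include centre in the imputation model.
- Delete the sentence that lets a mixed model replace the test. Keep the unadjusted t-test as a named sensitivity analysis, and the mixed model too if it is wanted, with its fixed effects and covariance structure stated.

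Baseline BMI is an optional further covariate; if used, it should be named in advance. If the sponsor prefers the t-test as primary, the minimum repair is to delete the mixed-model sentence.

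The cost is a few sentences, with no new data or subjects, and about 0.3 point of power or less at the 5% margin if centre explains nothing.
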